## List of Abbreviations

AE	adverse event
ALT	alanine aminotransferase
AST	aspartate aminotransferase
AUDIT	Alcohol Use and Disorders Identification Test
CARDIA	Coronary Artery Risk Development in Young Adults
CFR	Code of Federal Regulations
CBC	Complete blood count
CFR	Code of Federal Regulations
CRF	case report form
CTCAE	Common Terminology Criteria for Adverse Events
DHEAS	Dehydroepiandrosterone
DMC	Data Monitoring Committee
DSMB	Data Safety Monitoring Board
eCRF	electronic case report form
EDC	Electronic Data Capture
EU	European Union
FDA	Food and Drug Administration
GCP	Good Clinical Practice
HbA1c	Hemoglobin A1c
HCV	Hepatitis C virus
HCV Ab	Hepatitis C virus antibody
HIPAA	Health Insurance Portability and Accountability Act of 1996
HIV	Human Immunodeficiency Virus
HOMA-IR	Homeostatic model assessment for insulin resistance
HRPP	Human Research Protection Program
ICF	informed consent form
ICH	International Council on Harmonisation
IEC	Independent Ethics Committee
IRB	Institutional Review Board
IND	Investigational New Drug
INR	International normalized ratio
LDL	low-density lipoprotein
LDL-R	low-density lipoprotein receptors
MeDRA	Medical Dictionary for Regulatory Activities
MRE	Magnetic Resonance Elastography
MRI	Magnetic Resonance Imaging
MRI-PDFF	Magnetic Resonance Imaging Proton Density Fat Fraction

NAFLD	Nonalcoholic Fatty Liver Disease
NAS	NAFLD Activity Score
NASH	Nonalcoholic Steatohepatitis
NF	National Formulary and Drug Standards Laboratory
PI	Principal Investigator
PCOS	Polycystic Ovary Syndrome
NIDDK	National Institute of Diabetes and Digestive and Kidney Diseases
SAE	serious adverse experience
SAP	Statistical Analysis Plan
SGOT	serum glutamic oxaloacetic transaminase
SGPT	serum glutamate pyruvate transaminase
UCSF	University of California San Francisco
U.S.	United States
USP	United States Pharmacopeial Convention, Incorporated

## PROTOCOL SYNOPSIS

TITLE	Pilot Randomized Controlled Trial of Spironolactone in Women With Nonalcoholic Steatohepatitis (NASH)
SPONSOR	[name]
FUNDING ORGANIZATION	NIDDK
NUMBER OF SITES	1
RATIONALE	
Nonalcoholic steatohepatitis (NASH), or fat-related liver inflammation and scarring is projected to be the leading cause of cirrhosis in the United States (U.S.) within the next few years. Women are at disproportionate risk for NASH, with approximately 15 million U.S. women affected. There is an urgent need to understand risk factors for NASH and its progression in women, and sex hormones may provide a missing link.
 
Our preliminary data support a detrimental role of androgens, or “male sex hormones” on fatty liver in women but no studies have evaluated whether androgens are associated with liver inflammation and/or scarring from fatty liver (aka NASH). To better understand the mechanism by which androgens might promote NASH and/or metabolic co-factors that contribute to NASH, we are conducting a pilot clinical trial to primarily assess the feasibility of using an androgen blocking medication, spironolactone, in women with NASH. Spironolactone was selected because it is has been commonly prescribed for decades with good safety profile and tolerability to treat symptoms of high androgens, like acne and hirsutism in women. Though primarily a feasibility-focused study, we also aim to explore the pathways by which blocking testosterone receptors might alter the biologic processes that promote NASH and its associated metabolic co-morbidities in women.

STUDY DESIGN	This is a single center, double-blind, placebo-controlled, randomized, (2:1) parallel group pilot clinical trial of spironolactone in women with biopsy-proven NASH receiving 6 to 12 months of spironolactone or placebo.
PRIMARY OBJECTIVES	To establish the feasibility and tolerability of the intervention and study outcomes measures.
SECONDARY OBJECTIVES	
 
• To examine the effect of spironolactone on features of NASH on MRE and MRI-PDFF
 
• To examine the effect of spironolactone on features of NASH on liver biopsy
 
• To examine the effect of spironolactone on metabolic parameters that contribute to NASH progression
 
• To examine the effect of spironolactone on sex hormone levels and androgen receptor expression in liver tissue
 

NUMBER OF SUBJECTS	30 total women: 20 randomized to spironolactone and 10 randomized to placebo
SUBJECT SELECTION CRITERIA	
Key Inclusion Criteria:
 
 
- Women with NASH identified on standard of care liver biopsy performed for clinical purposes.
 
 
Key Exclusion Criteria:
 
 
- Uncontrolled diabetes
 
- Alcohol consumption >2 drinks per day for at least 3 consecutive months over the previous 5 years
 
- Other chronic liver disease (i.e. hepatitis B virus, hepatitis C virus, autoimmune hepatitis) or cirrhosis from any cause
 
- Recent or planned upcoming weight reduction surgery within five years of diagnosis of biopsy-confirmed NASH
 
- HIV infection
 
- Drugs associated with fatty liver (i.e. amiodarone, methotrexate, systemic glucocorticoids, tamoxifen, anabolic steroids, valproic acid) for more than 4 weeks prior to baseline or during study
 
- Recent, current, or planned upcoming pregnancy or current perimenopausal status
 
- Renal impairment (glomerular filtration rate <45 ml/min/1.73m or potassium levels > 5.0 mmol/L)
 
- Androgen receptor antagonist use (i.e. flutamide, spironolactone or flutamide) for more than 3 months within one year prior to baseline
 

TEST PRODUCT, DOSE, AND ROUTE OF ADMINISTRATION	Spironolactone 100mg. Product will be administered orally once daily for a length of 6 to 12 months.
CONTROL PRODUCT, DOSE AND ROUTE OF ADMINISTRATION	Placebo. Product will be administered orally once daily for a length of 6 months.
DURATION OF SUBJECT PARTICIPATION AND DURATION OF STUDY	
Subjects will be on study for up to 10 or 16 months
 
Screening: up to one month
 
Treatment: 6 to 12 months
 
Follow-up: up to 3 months from end of treatment
 
The total duration of the study is expected to be 4 years. Women will be enrolled and treated on a rolling basis, with a 30 month total recruitment period, 6 to 12 months of treatment per participant, and up to 3 months for the final subject follow-up post treatment.

CONCOMMITANT MEDICATIONS- PROHIBITED	
 
- Androgen receptor antagonists (i.e. flutamide or flutamide) including current use of spironolactone
 
- Eplerenone as also blocks aldosterone receptor
 
- Drugs associated with fatty liver (i.e. amiodarone, methotrexate, systemic glucocorticoids, tamoxifen, anabolic steroids, valproic acid)
 

EFFICACY EVALUATIONS	
As a pilot trial this study is not powered to detect an effect of spironolactone on NASH progression in women. The primary goal of the study is rather to evaluate the feasibility and tolerability of the study intervention and outcome measures in women with NASH while also exploring the mechanisms by which blocking testosterone receptors may alter NASH severity or associated metabolic comorbidities leading to NASH. If the intervention is deemed to be feasible, and we detect a signal that spironolactone may alter these biologic processes, then these data would be used to support a larger trial aimed at assessing the efficacy of spironolactone or other related androgen modulating medication on the treatment of NASH in women.

PRIMARY ENDPOINTS	
Feasibility endpoints:
 
 
• Adherence and acceptability of spironolactone in women with NASH
 
• Adherence and acceptability of study outcome measures (MRI and optional EOT biopsy)
 
 
Determine the range of NASH on baseline biopsy to inform inclusion criteria for larger trials

SECONDARY ENDPOINTS	
 
• Biochemical endpoints: serum lipids, HOMA-IR, liver enzymes
 
• Radiologic endpoints: liver fat quantity, visceral fat volume, liver inflammation, liver scarring
 
• Histologic endpoints: Change in NAFLD Activity Score (NAS)
 
• Expression of androgen receptors in the liver and circulating hormone levels.
 

SAFETY EVALUATIONS	
Spironolactone is an old, commonly used medication to treat symptoms of high androgens in women therefore has a longstanding favorable side effect profile. Change in clinical safety labs and in person review of potential side effects will be assessed at each study visit. Incidence of adverse events will be collected.

PLANNED INTERIM ANALYSES	The Data Safety Monitoring Board (DSMB) will review the progress of the study and perform an interim review of the safety data after the first 10 participants have completed 3 months of spironolactone, or at any time that a comprehensive review of safety is felt to be necessary. The committee will provide recommendations to [name] whether the nature, frequency, and severity of adverse effects associated with study treatment warrant the early termination of the study in the best interests of the participants, whether the study should continue as planned, or the study should continue with modifications. The DSMB may also provide recommendations as needed regarding study design, or changes to study conduct.
STATISTICS Primary Analysis Plan	The focus of the pilot trial will be feasibility testing and obtaining preliminary assessments of the effects of spironolactone. Exact 95% confidence intervals for rates of agreement to participate, meeting eligibility criteria, completing follow-up will be calculated using the binomial distribution. Between-group analyses will be performed according to the intention-to-treat principle. We will attempt to collect complete follow-up data on every randomized participant, regardless of adherence to treatment. As randomization in this small sample may not result in the perfect balance of relevant biological variables (e.g., age or weight between groups) we will perform analyses adjusting for any of these that are substantially imbalanced. A planned interim analysis will be conducted after the first 10 participants (25%) have completed 3 months of spironolactone. Interim results will provide useful preliminary safety and feasibility data.
Rationale for Number of Subjects	The sample size of 30 was determined based on budget and feasibility within a 4-year grant timeline. The sample size is also reasonable for pilot trial, and will allow us to estimate effects and feasibility with reasonable precision.

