### **4 STUDY DESIGN**

#### **4.1 Study Overview**

This is a single center, double-blind, placebo-controlled, randomized (2:1), parallel group pilot clinical trial. 30 women are targeted for enrollment. Each participant will be administered a single dose of spironolactone or placebo once daily for a total of 6 months. In person evaluations will take place at Month 1, 3, 6, and at the follow up visit within 3 months of end of treatment (up to Month 9). Participants may opt to extend the

study treatment period to 12 months. Participants who opt to extend will complete additional in person evaluations at Month 9 and Month 12. Screening data will be reviewed to determine subject eligibility. Subjects who meet all inclusion criteria and none of the exclusion criteria will be entered into the study.

The following treatment regimens will be used:

- Experimental treatment – spironolactone, 100 mg once daily
- Placebo or Comparator – one capsule, once daily

Total duration of study treatment will be 6 months or 12 months. Total duration of the study is expected to be  $\leq 10$  or  $\leq 16$  months (including up to 1 month for screening).

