#### **10.6 Optional Visits (if subject opts to extend study period)**

- Month 9 visit will include the same evaluations as listed for Visits 3 and 4
- Month 12 Visit will serve as the end of study/treatment visit (liver biopsy will be completed at Month 12 instead of Month 6 if subject wishes to extend study period).

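### The synopsis control-product row gives placebo for 6 months, contradicting every other statement on the extension; separately, an extender's biopsy moves to Month 12 on either reading

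*Combined protocol and SAP*

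**What the plan says.** Two adjacent rows of the Protocol Synopsis give durations specific to an arm. The control-product row says "Placebo. Product will be administered orally once daily for a length of 6 months". The test-product row says "Product will be administered orally once daily for a length of 6 to 12 months".

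Every other statement on duration either names both arms or does not separate them:

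- Synopsis, Study Design: women are described as "receiving 6 to 12 months of spironolactone or placebo".
- Synopsis, duration of participation: "Subjects will be on study for up to 10 or 16 months", with "6 to 12 months of treatment per participant".
- Section 4.1: six months is the base period for spironolactone or placebo, and participants may then choose to extend. "Participants who opt to extend will complete additional in person evaluations at Month 9 and Month 12". The section closes with "Total duration of study treatment will be 6 months or 12 months".
- Section 10.6 and Appendix 1: Months 9 and 12 are scheduled for any subject who extends.

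On blinding, Section 8.2 keeps investigators, staff and patients unaware of assignment until the study is complete and the database is locked. It names pregnancy as the only condition certain to lead to unblinding.

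On biopsy timing, Section 10.6 says "liver biopsy will be completed at Month 12 instead of Month 6 if subject wishes to extend study period". Section 9.3 and Appendix 1 make that biopsy optional. MRE and MRI-PDFF (Section 9.4) and sex hormones (Section 9.2.3) are measured at Month 6 in everyone and again at Month 12 in extenders. Blood chemistry is drawn at each visit (Section 9.2.1).

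**The concern.** There are two separate problems.

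The first is the contradiction. In a double-blind trial, a treatment duration that differs by arm cannot be carried out without disclosing the arm. The investigational pharmacy selects capsules according to the randomization schedule and supplies them three months at a time (Section 8.4.3), so it could act on an arm-specific duration. Section 8.4 does not say what is supplied after Month 6. If the control row were followed, a woman given extension capsules would be known to be on spironolactone, and a woman refused them would be known to be on placebo. Enrollment is rolling over 30 months at one site, so this would occur while other women were still being recruited and followed. Dropout is among the primary feasibility endpoints in Section 5.1, and knowledge of the arm could influence it.

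The second problem does not depend on the first. A woman who extends has no Month 6 histology, because her biopsy replaces the Month 6 one. Whether she extends is her own choice after randomization. Sections 5.2 and 15.4 define and analyze change in NAS and receptor expression without naming a visit. Six-month and 12-month biopsies could therefore enter one comparison, which would mix drug effect with length of exposure and with whatever led women to extend.

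**Working it through.** **Stated figures.** Screening is up to 1 month, treatment 6 or 12 months and follow-up up to 3 months (synopsis). 1 + 6 + 3 = 10 and 1 + 12 + 3 = 16, which reproduces the stated 10 or 16 months. The 16-month figure is not confined to one arm. Allocation of 30 women at 2:1 gives 30 × 2/3 = 20 and 30 × 1/3 = 10, as stated.

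**Reading A: the control row applied literally.** All women on treatment after Month 6 are on spironolactone, so the probability that a continuing woman is on spironolactone is 1, against 2/3 at randomization. If a share f of the spironolactone arm continues, the probability that a woman who stops at Month 6 is on placebo is 10/(30 − 20f), against 1/3 at randomization. Month 12 has 20f spironolactone and 0 placebo women, so no contrast can be estimated.

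**Reading B: the extension open to both arms.** Continuing does not by itself identify the arm. With equal uptake f, Month 12 has 20f and 10f women. The standard error of a mean difference, in SD units, is √(1/(20f) + 1/(10f)).

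The documents give no uptake, so f is assumed over a range:

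| f | Spironolactone, Month 12 | Placebo, Month 12 (A) | P(placebo, given stop at Month 6) (A) | Placebo, Month 12 (B) | SE/SD at Month 12 (B) |
|---|---|---|---|---|---|
| 0.25 | 5 | 0 | 0.40 | 2.5 | 0.775 |
| 0.50 | 10 | 0 | 0.50 | 5 | 0.548 |
| 0.75 | 15 | 0 | 0.667 | 7.5 | 0.447 |
| 1.00 | 20 | 0 | 1.00 | 10 | 0.387 |

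**Biopsy timing.** Suppose first that every woman has the biopsy. Mean exposure at biopsy in an arm with extension share f is 6(1 − f) + 12f = 6 + 6f months.

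- Reading A: placebo stays at 6 months, so the arms differ by 6f months. That is 1.5, 3 and 4.5 months for f = 0.25, 0.50 and 0.75.
- Reading B: the arms differ by 6 × (f in spironolactone − f in placebo) months. This is zero if uptake is equal. It is 6 × (0.75 − 0.25) = 3 months if uptake were 75% and 25% (assumed). Even with equal uptake, each arm is a mixture of 6- and 12-month biopsies.

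Because the biopsy is optional, the counts in the table are ceilings for biopsies at Month 12.

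**Cost of separating the visits (reading B, equal uptake).** Month 6 histology would have at most 20(1 − f) and 10(1 − f) women. That is 15 and 7.5, 10 and 5, or 5 and 2.5 for f = 0.25, 0.50 and 0.75, with SE/SD of at least 0.447, 0.548 and 0.775. With all 30 biopsied at one visit it would be √(1/20 + 1/10) = 0.387.

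**Endpoints not affected.** Imaging, hormones and chemistry are scheduled at Month 6 whether or not a woman extends, so their Month 6 comparisons do not depend on uptake or on where the biopsy falls.

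**The case against.** The strongest reply is that one synopsis cell is out of line and the design is clear. Section 4.1, which defines the extension, opens it to participants without regard to arm. The synopsis Study Design row names placebo explicitly. Capsules and labels are identical, and the pharmacy can dispense blinded capsules in both arms after Month 6. Section 4.1 itself describes 6 months as the base period for both arms, so the control row may state only that base. Much of this stands. It means that unblinding and loss of the Month 12 control group are conditional consequences. It does not remove the contradiction: the test-product row was written to cover the extension and the control row beside it was not, so the difference can be read as intended.

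A reader might infer more: that the synopsis confines the extension to spironolactone, so that the extension as designed unblinds the trial and Month 12 has 20 women against none. The documents do not support that. It takes one row as the design against several others, and it would also breach Section 8.2. Nor do they support the idea that final imaging has lost its Month 6 comparison, since Section 9.4 keeps the Month 6 scan for everyone.

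On histology, it is fair to say that no text states that Month 6 and Month 12 biopsies will be pooled, that a detailed SAP is still to be written (Section 15), and that histology is secondary in a pilot not powered for efficacy. The timing problem is therefore a gap to close, not an error already committed.

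**Conclusion.** The control-product row contradicts the test-product row, the Study Design and duration rows of the synopsis, Sections 4.1 and 10.6, and Appendix 1. This is a real inconsistency about treatment duration in a blinded trial.

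Its consequence depends on which text is followed. Applied literally, the control row would disclose the arm of every woman who asked to extend and would leave at most 20 spironolactone and 0 placebo women on treatment at Month 12. Under the other statements, extending does not disclose the arm and up to 10 placebo women could reach Month 12.

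On either reading, an extender's optional biopsy falls at Month 12 instead of Month 6 by her own choice. Change in NAS and in liver androgen receptor expression could then mix 6- and 12-month exposure. With assumed uptake of 25% to 75%, up to 5 to 15 of the 20 spironolactone women would have the later biopsy. Up to 2.5 to 7.5 of the 10 placebo women would too if both arms extend equally, and none under the control row. Month 6 imaging, hormone and biochemical comparisons are unaffected.

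**What to change.** 1. Reconcile the control-product row with the test-product, Study Design and duration rows of the synopsis, Sections 4.1 and 10.6, and Appendix 1. The documents should state treatment duration and extension consistently, in a way compatible with the blinding in Section 8.2, and Section 8.4 should carry the same statement for supply after Month 6. This review does not say which duration is right.
2. In the SAP, report change in NAS and in androgen receptor expression by visit and arm, giving the number of biopsies in each cell. Do not pool Month 6 and Month 12 biopsies into one NAS or receptor-expression comparison unless that breakdown is shown beside it.

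The cost is wording changes and smaller numbers per histology comparison. At 50% uptake in both arms, for example, each visit would have at most 10 and 5 biopsies. No additional women or visits are needed.

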### **5.3 Safety Evaluations**

- In-person visits will be conducted at baseline, at one month (given highest risk of adverse events in first month of drug exposure) and every 3 months thereafter. Additionally women will be seen within 3 months after end of treatment to ensure resolution of any drug related side effects. In-person study visits will include a physical exam with vital signs, anthropomorphic measurements, assessment of adherence with pill counts, assessment of side effects, and performance of safety monitoring labs including electrolytes, renal function and urine pregnancy tests. Each visit will also include contraceptive counseling for pre-menopausal women because spironolactone has potential risk of feminization seen in animal studies of male fetuses, though no studies have implicated spironolactone in these birth defects in humans. Pregnancy testing will be performed every month to ensure that if a participant were to become pregnant, spironolactone is discontinued within 4 weeks of conception. This will ensure no fetal risks as human sex organ development begins between 6-8 gestational weeks.
- There will be continuous safety surveillance of participants through the reporting of incidence of adverse events (AEs). AEs will be recorded in a systematic manner at every study visit and when otherwise volunteered by the participant.

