## **14 DATA SAFETY MONITORING**

The Data Safety Monitoring Board (DSMB) will include one reproductive endocrinologist ([name]) and one hepatologist ([name], MD) who are UCSF faculty who are not directly involved in the study itself, but have expertise in use of spironolactone to treat elevated androgens in women, and expertise in liver disease respectively. This DSMB will review data relating to safety and efficacy, conduct and review interim analyses, and ensure the continued scientific validity and merit of the study. Further details regarding the timing and content of the interim reviews is included in the statistical section below.

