### **15.5 Interim Analysis**

Planned interim analyses will be conducted after 10 women (~33%) have completed three months of treatment. Interim results will provide useful preliminary safety and feasibility data.

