### **15.6 Sample Size and Randomization**

The sample size of 30 with 2:1 randomization was determined based on budget and feasibility within a 4-year grant timeline. The sample size is also reasonable for pilot trial, and will allow us to estimate effects and feasibility with reasonable precision. The 2:1 randomization was selected to increase the chance that women would receive the treatment, and therefore potentially increase study enrollment, while still allowing the investigator to obtain the necessary training in conducting a placebo-controlled trial in preparation for a larger trial in the future, and allowing for preliminary endpoint assessments in the treatment as compared to placebo groups.

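### Does calling the 10-woman interim look 25% of the trial, when 10 of 30 is 33%, require a change to the plan?

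*Combined protocol and SAP*

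**What the plan says.** Three sentences describe the interim look.

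- Synopsis, Primary Analysis Plan: "A planned interim analysis will be conducted after the first 10 participants (25%) have completed 3 months of spironolactone".
- Synopsis, Planned Interim Analyses, on what the DSMB will do: "perform an interim review of the safety data after the first 10 participants have completed 3 months of spironolactone". No percentage is given.
- Section 15.5: "Planned interim analyses will be conducted after 10 women (~33%) have completed three months of treatment".

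The sample size is consistent. The synopsis has "30 total women: 20 randomized to spironolactone and 10 randomized to placebo", Section 4.1 has "30 women are targeted for enrollment", and Section 15.6 has "The sample size of 30 with 2:1 randomization was determined based on budget and feasibility within a 4-year grant timeline". The synopsis row on the number of subjects, directly below the 25%, also gives 30.

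Section 14 tells the reader where the timing is defined: "Further details regarding the timing and content of the interim reviews is included in the statistical section below". The synopsis also lets the DSMB carry out a full safety review whenever it thinks one is needed.

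**The concern.** Two current passages give different fractions for the same look, and only one can be right for a total of 30. In a trial with a group-sequential boundary, a wrong information fraction would put the wrong critical value on the interim test, so a mismatch of this kind deserves a check.

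The wording of the trigger adds a second doubt. The synopsis counts women who have had 3 months of spironolactone, and Section 15.5 counts women who have had three months of treatment. Under 2:1 allocation these are different counts if the synopsis is taken at its word. The synopsis names both products when it describes the design, so its authors could distinguish the arms when they wished to. Someone working from the synopsis alone might misjudge how far the trial had run, or might wait for 10 women on active drug before convening the DSMB.

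**Working it through.** **Inputs.** Total 30, with 20 on spironolactone and 10 on placebo (synopsis; Sections 4.1 and 15.6). Interim count 10 (synopsis; Section 15.5). Exposure at the look 3 months, full treatment 6 months with an optional extension to 12 (Section 4.1).

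**Percentage.**

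1. Share of all randomized women: 10/30 = 33.3%. This reproduces Section 15.5.
2. The synopsis figure applied to the stated total: 0.25 × 30 = 7.5 women, not 10.
3. Total implied by the synopsis figure: 10/0.25 = 40, which appears nowhere in the available text.
4. Share of the spironolactone arm: 10/20 = 50%.
5. Enrolment inflated for dropout, 30/(1 − d), rounded up. No dropout rate is stated, so d is assumed: 10% gives 34, 15% gives 36, 20% gives 38. Only 25% gives 40. Section 12.3 provides for replacing women who withdraw from treatment, but this does not create a planned total of 40.
6. Person-months in the active arm: (10 × 3)/(20 × 6) = 30/120 = 25%. This is the only route from documented inputs to the synopsis figure. It does not fit, because the synopsis attaches 25% to a number of participants and mentions no exposure fraction. Over all 30 women the same calculation gives 30/180 = 16.7%, and over the active arm at 12 months it gives 30/240 = 12.5%. The match looks like coincidence.

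The 25% is therefore an error, and the correct figure is already in Section 15.5.

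**Trigger wording.**

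1. If spironolactone means study drug, both texts count 10 women in either arm. About 10 × 20/30 = 6.7 of them would be on spironolactone.
2. If it is literal and nobody stops early, 10/(20/30) = 15 randomized women are needed to supply 10 completers on active drug. The block size is not stated. For 20 active and 10 placebo assignments in random order, the 10th active assignment falls on average at position 10 × 31/21 = 14.8.
3. These are the women who supply the completers, not everyone randomized by the time of the look. Assuming uniform accrual of 30 women over the 30-month recruitment period, about 1 a month, some 3 more would enter during the 3 months. That gives about 18 against 13, and the gap of about 5 is unchanged.

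Usage elsewhere gives mixed guidance. Section 5.3 says of any participant: "if a participant were to become pregnant, spironolactone is discontinued within 4 weeks of conception". That suggests loose use of the drug name, but fetal risk is specific to spironolactone, so it could also be literal. Section 9.2.2 says study drug for the same event.

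**What depends on either.** The primary analysis is a set of exact binomial confidence intervals (Section 15.3), and the trial is not powered for efficacy. Section 14 lets the DSMB see efficacy as well as safety data, but the plan attaches no alpha, boundary or information fraction to the look. The DSMB's recommendation rests on the nature, frequency and severity of adverse effects, and none of these uses the fraction enrolled.

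**The case for a change.** The best case for acting is that this is the only look with a scheduled trigger, that the DSMB may recommend early termination from it, and that its timing should read the same everywhere. Correction would take a few words. Section 15 says a detailed SAP is still to be written, so an unreconciled text could carry the wrong fraction or an ambiguous trigger forward. A literal active-arm count would also need access to the randomization code.

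Part of this stands. The percentage is wrong, and the two descriptions of exposure are not identical. If an active-arm count was intended, neither 25% nor 33% describes it, since 10/20 = 50%.

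The rest carries little weight. The SAP's authors will work from the statistical section, where the figure is right. The pharmacy generates the randomization table and assigns capsules from it (Sections 8.1 and 8.4), so an arm-specific count would not require unblinding study staff. Writing in that the 10 women are counted across both arms would go beyond the documents, because Section 15.5 does not say so. It would settle an open safety-review trigger in favour of about 6.7 rather than 10 women with 3 months on active drug. That choice belongs to the sponsor and the DSMB and cannot be derived from the text.

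**Conclusion.** The contradiction is real but clerical. The synopsis figure should read about 33%, a difference of 33.3 − 25 = 8.3 percentage points in a label that nothing uses. The operative number, 10 women, is the same throughout, and Section 14 points to the section that has the fraction right. Correcting it at the next edit is good housekeeping but would alter no analysis, decision or conclusion.

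The wording of the trigger makes no difference on the likelier reading. On the literal one it moves the look later by about 5 randomized women. The sponsor should reconcile the passages and say which count is meant. Until then the DSMB's freedom to review safety at any time limits the consequence.

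This conclusion rests on a planned total of 30 and on the absence of any stopping rule tied to the fraction. It does not depend on which reading of the trigger is right. The counts for the literal reading assume no early stopping, and those for women randomized by the time of the look also assume uniform accrual.
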